## **9.7. Accountability Procedures for the Study Intervention/Investigational Product**

The site principal investigator (PI) (or designee) will maintain an accurate record of the receipt of the investigational materials as shipped, including the date received. One copy of this receipt will be returned to OpenBiome when the contents of the investigational materials shipment have been verified. In addition, the unblinded laboratory technician based at OpenBiome will maintain a log of all clinical trial materials (DE and placebo) dispensed. This clinical trial material accountability record will be available for inspection at any time.

Participants in the daily FMT or placebo groups will be given a diary to record when doses are taken and number of doses remaining. This diary will be collected after participants complete the treatment portion of the study. Study staff will attempt to collect any remaining study capsules from the participants in person or via mail as appropriate, and this accountability will be reviewed by the Infectious Disease Research Lab.

## **9.8. Modification of Study Intervention/Investigational Product for a Participant**

If the participant is unable to complete the full dose of DE or placebo in one sitting the actual dose ingested will be recorded. Further study product administration, including the remainder of the incomplete dose and scheduled upcoming doses as applicable will be at the discretion of the treating physician. The remaining capsules scheduled to be administered may be offered to the participant on the same day they were scheduled. Intention-to-treat analysis will be utilized according to best practices in clinical trials.

## **9.9. Concomitant Medications/Treatments**

Given our patient population is likely to have multiple comorbidities, all medications except those listed in the exclusion criteria will be accepted in this study, at the discretion of the treating physician. Though the exclusion criteria lists antibiotics used for more than 72 hours as an exclusionary medication, patients on long-term antibiotics – such as prophylactic Bactrim, azithromycin, or doxycycline – are eligible at the discretion of the study physician. This includes, but is not limited to:

1. Long-term antibiotics (one month or more, e.g. prophylactic Bactrim, azithromycin, or doxycycline)
2. Anti-hypertensive therapies
3. Heart failure medications
4. Diuretics
5. Laxatives
6. Topical medications
7. Anti-depressants
8. Statins
9. Diabetic medication

10. Non-steroidal Anti-inflammatory Drug (NSAID)
11. Acid-blockers
12. Anticoagulants
13. Opioids
14. Iron supplementation
15. Anti-TNF will be permitted. Patients on monoclonal antibodies to B and T cells, glucocorticoids, antimetabolites (azathioprine, 6-mercaptopurine, methotrexate), calcineurin inhibitors (tacrolimus, cyclosporine) and mycophenolate mofetil may be enrolled only after consultation with the medical monitor.

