## 2. STUDY SUMMARY

Title	A phase II randomized, double-blind placebo-controlled trial to determine if fecal microbiota transplantation is efficacious for hospitalized patients with C. difficile infection history during antibiotic treatment
Short Title and Precis	The GRAFT study
Protocol Number	2017-0789
ClinicalTrials.gov number	NCT03621657
Funding Sponsor	Agency for Healthcare Research and Quality (AHRQ) [name] [contact]
Study Product	OpenBiome fecal microbiota preparation capsule [FMT Capsule DE]
Phase	Phase II study
Methodology	Randomized, double-blind, placebo-controlled trial
Study Duration	1 year
Study Center(s)	Single-center, University of Wisconsin Hospitals and Clinics
Objectives	The primary objective of this study is to compare the gut microbiota and clinical outcomes of oral FMT during antibiotic treatment, immediately following antibiotic treatment, and placebo. The second objective is to assess the safety and feasibility of daily oral Fecal Microbiome Transplant (FMT) as a treatment option.
Number of Subjects	30 (1:1:1 randomization), 10 subjects per group
Diagnosis	Changes in the gut microbiota and C. difficile infection (CDI)
Main Inclusion Criteria	Receiving antibiotics for reasons other than CDI following a recent CDI episode (within last 90 days)
Main Exclusion Criteria	Bowel obstruction or gut motility issues, severely immunocompromised, or admitted to the ICU.
Study Product, Dose, Route, Regimen	FMT will be delivered through oral capsules prepared by OpenBiome. It will be administered in one of two ways depending on the arm of the trial. 1) A low dose of 5 capsules per day during antibiotic treatment and for seven days following conclusion of antibiotics. 2) A single dose of 30 capsules (22.5g) of oral FMT will be given 48-72 hours after antibiotic treatment conclusion.
FDA status of product	Encapsulated fecal microbiota preparation (FMT Capsule DE). Please refer to Finch Therapeutics BBMF # 17194.
	Sourced from human-derived microbes. Please refer to OpenBiome BBMF # 15543, Section F.
	IND: 18262

**Duration of administration** Group 1: 5 capsules of oral FMT per day undergoing antibiotic treatment and for 7 days following conclusion of antibiotic treatment.

Group 2: 30 capsules taken 48-72 hours following conclusion of antibiotic treatment

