### **8.2. Inclusion Criteria**

1. Cognitively intact and willing to provide informed consent.
2. Willing and able to comply with all study procedures for the duration of the study.
3. Able to take oral medications.
4. Age 18 or over.
5. Recent CDI episode occurring in the last 90 days with completion of therapy as confirmed by the electronic medical record (EMR)
6. Receiving antibiotics at enrollment for reasons other than CDI and having taken the antibiotics for no longer than 72 hours.
7. Women of childbearing potential in a sexual relationship with men must use an acceptable method of contraception (including, but not limited to, barriers with additional spermicidal foam or jelly, intrauterine devices, hormonal contraception started at least 30 days before enrollment into the study, or intercourse with men who underwent a vasectomy) for 4 weeks following completion of the study treatment.
8. Males must agree to avoid impregnation of women during and for 4 weeks following completion of the study treatment.
9. Able to take the test capsule successfully with no signs or symptoms of dysphagia.\*

\*For patients not receiving treatment during the enrollment visit, the ability to successfully swallow the test capsule can be confirmed the day the intervention is administered.

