### **8.3. Exclusion Criteria**

1. Admitted to an intensive care unit (ICU).
2. Females who are pregnant, lactating, or planning to become pregnant during the study. Female patients of childbearing potential will take a pregnancy test at the intervention visit and will be excluded if pregnant.
3. Inability (e.g. dysphagia) to or unwilling to swallow capsules.
4. Known or suspected toxic megacolon and/or known small bowel ileus.
5. Bowel obstruction or other gut motility issues occurring in the last two weeks that are unresolved as noted by the patient or in the EMR.
6. Major gastrointestinal surgery (e.g. significant bowel resection) within 3 months before enrollment not including appendectomy or cholecystectomy.
7. History of bariatric or colectomy surgery.

8. Concurrent intensive induction chemotherapy, radiation therapy, or biologic treatment for an active malignancy. Patients on maintenance chemotherapy may be enrolled after consultation with the medical monitor.
9. Expected life expectancy <6 months.
10. Patients with severe anaphylactic or anaphylactoid food allergy.
11. Solid organ transplant recipients ≤90 days post-transplant or on active treatment for rejection.
12. Neutropenia ( $\leq 500$  neutrophils/mL) or other severe immunosuppression. Anti-TNF will be permitted. Patients on monoclonal antibodies to B and T cells, glucocorticoids, antimetabolites (azathioprine, 6-mercaptopurine, methotrexate), calcineurin inhibitors (tacrolimus, cyclosporine), and mycophenolate mofetil may only be enrolled after consultation with the medical monitor.\*
13. At risk of CMV/EBV associated disease, negative IgG testing for cytomegalovirus (CMV) or Epstein Barr Virus (EBV).
14. Any other gastrointestinal illness including diarrhea.
15. On oral vancomycin or metronidazole.
16. Having been taking the currently prescribed antibiotic for over 72 hours.
17. On an antibiotic treatment anticipated to exceed 19 days.
18. Having received an FMT by any route in the 90 days prior to enrollment.
19. Any condition that would jeopardize the safety or rights of the patient, would make it unlikely for the patient to complete the study, or would confound the results of the study.

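### Section 9.9 admits patients on antibiotics of a month or more without addressing the 19-day exclusion, and no section says which antibiotic governs eligibility and dosing

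*Combined protocol and SAP*

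**What the plan says.** **Eligibility lists.** Inclusion 6 (section 8.2) requires "Receiving antibiotics at enrollment for reasons other than CDI and having taken the antibiotics for no longer than 72 hours". Exclusion 16 (section 8.3) removes anyone "Having been taking the currently prescribed antibiotic for over 72 hours". Exclusion 17 removes anyone "On an antibiotic treatment anticipated to exceed 19 days". None of the three carries an exception.

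**Concomitant medications.** Section 9.9 accepts all medications other than those named in the exclusion criteria. It then makes an exception, opening "Though the exclusion criteria lists antibiotics used for more than 72 hours as an exclusionary medication" and going on to say that patients on long-term antibiotics "are eligible at the discretion of the study physician". Item 1 of its list reads "Long-term antibiotics (one month or more, e.g. prophylactic Bactrim, azithromycin, or doxycycline". Exclusion 17 is not mentioned.

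**Dosing clocks.** Section 7.1 ties dosing to the antibiotic course in every arm. Groups 1 and 3 take capsules on each antibiotic day and for 7 days more. For Group 2 the Study Summary gives "Group 2: 30 capsules taken 48-72 hours following conclusion of antibiotic treatment".

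**Long regimens.** Section 8.4.2.2 has a fallback for regimens longer than 14 days: daily dosing stops at day 14, and the 30-capsule dose is given on day 16 or 17.

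**Analysis.** The Study Summary and section 12.3 name no covariate, subgroup or sensitivity analysis for antibiotics that continue after the intervention.

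**The concern.** Two operative rules give opposite answers for one patient. Section 9.9 lets in a patient on, say, long-term prophylaxis; exclusion 17, applied as written, removes the same patient. Staff who verify eligibility from sections 8.2 and 8.3 would not find the exception at all.

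The second gap is the phrase antibiotic treatment itself. Eligibility, dosing and the 14-day cutoff all depend on it, yet no operative section says which drug is meant when a patient takes a long-term agent and also starts a new one. Section 9.9 does not say that a new course is needed as well.

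At stake is the contrast the trial was built for. The primary objective in the Study Summary compares FMT during antibiotics, FMT just after antibiotics, and placebo, with gut microbiota as the primary outcome. Antibiotic exposure acts directly on that outcome. Patients whose exposure does not end would be mixed, unmarked, with patients whose exposure does.

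**Working it through.** The plan states no figure on this point, so the check is a comparison of rules with day counts.

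**Step 1. Long-term use against each limit.** A month is at least 28 to 31 days.

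| Rule | Limit | 28 days against it | Does 9.9 address it? |
|---|---|---|---|
| Inclusion 6 | 72 h = 3 days | exceeds | In substance (same 72-hour limit), but no exception printed in 8.2 |
| Exclusion 16 | 72 h = 3 days | exceeds | Yes, expressly; not printed in 8.3 |
| Exclusion 17 | 19 days | exceeds by 28 − 19 = 9 days or more | No |
| Fallback, 8.4.2.2 | 14 days | exceeds by 28 − 14 = 14 days or more | No |

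The exclusion 17 row takes total treatment length, which is the literal reading. If only days still to come were counted, a finite course near its end could fall under 19; the text does not say so.

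**Step 2. The fallback.** Its own arithmetic is right: 14 + 2 = day 16 and 14 + 3 = day 17. It does not settle the question, because it too counts antibiotic days without saying of which drug. Its group labels also disagree with sections 7.1 and 9.6: it prints the 30-capsule dose under Group 1, the daily arm, and the end of daily dosing under Groups 2 and 3, although Group 2 is the single-dose arm.

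**Step 3. The two readings.**

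- *Reading A: the long-term drug is the governing antibiotic.* Days 14 to 17 may be past before enrollment. If the drug is not stopped, neither the 7 extra days nor the 48–72 hour window has a starting point.
- *Reading B: the long-term drug is background and a new course, started within 72 hours, governs.* Every trigger works as written, and the fallback covers long courses. But Group 2's dose, placed after the new course, is then given while the background antibiotic continues, as may be the 4 weekly follow-up stools in any arm.

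These consequences belong to different readings and cannot both be charged to the same patient.

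**Step 4. Possible size.** Sections 8.1 and 12.2 give 10 enrolled and 8 analyzed per group. One such patient is 1/10 = 10% or 1/8 = 12.5% of an arm. How many would enter is not stated. As an assumption only, take 1 to 3 of 30, that is 1/30 = 3.3% to 3/30 = 10%. Treating every 10/10/10 allocation as equally likely:

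- One patient: the chance of falling in Group 2 is 10/30 = 33%, and the arms are necessarily uneven.
- Three patients: the chance of at least one in Group 2 is 1 − C(20,3)/C(30,3) = 1 − 1140/4060 = 72%. The chance of exactly one per arm is 10 × 10 × 10/4060 = 25%, so the spread is uneven about 75% of the time.

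**The case against.** The best defense is that Reading B is the natural one. Item 1 stands in a concomitant-medication list beside statins and diuretics. Exclusion 16 speaks of the antibiotic currently prescribed. Section 8.4.1 aims at courses of two weeks or fewer, and section 8.4.2.1 tells patients with recent CDI to make contact if antibiotics are later prescribed. The revision log, though not operative text, points the same way. On this reading the plan needs only a clarifying sentence.

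Much of this stands, and it rules out several stronger inferences:

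- *That dosing cannot be applied in any arm.* This follows only under Reading A, and it overlooks the 14-day fallback.
- *That these patients' antibiotics have no end.* A month or more includes finite courses; continuing use is inferred.
- *That exclusions 16 and 17 are contradicted alike.* The 72-hour clash is an acknowledged exception. Only exclusion 17 is left unaddressed.
- *That sites would decide differently.* The trial has one center.
- *That the comparison is biased.* Allocation is randomized, so uneven spread is chance imbalance and noise.

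Two things survive. Exclusion 17, applied literally, still removes patients whom 9.9 admits. And Reading B does not restore the after-antibiotics contrast: it is the reading under which the Group 2 dose and follow-up stools can fall under continuing exposure, with no planned analysis to separate them.

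**Conclusion.** The point holds in a bounded form. Section 9.9 conflicts with exclusion 17 without saying so, its 72-hour exception is missing from the lists used to verify eligibility, and the antibiotic that governs eligibility and the dosing clocks is undefined. These follow from the text, with the literal reading of exclusion 17 as the only assumption.

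The effect on the primary comparison is conditional. It needs such patients to be enrolled and their antibiotics to continue through follow-up. The documents give no rate. Transplant clinics are a named recruitment source, which makes long-term prophylaxis plausible but supplies no number. If it happens, each patient is 10 to 12.5% of an arm, and the result is a diluted during-versus-after contrast and possible chance imbalance. The sample size of 30, which section 12.1 does not base on a hypothesis test, and the 0.05 level are unaffected. This should be corrected, but it does not undermine the design.

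**What to change.** 1. Define one index antibiotic and write inclusion 6, exclusions 16 and 17, the dosing triggers in section 7.1 and the Study Summary, and the 14-day cutoff in 8.4.2.2 against it. Reconcile the group labels in 8.4.2.2 with sections 7.1 and 9.6 in the same edit.
2. State in section 8.3 whether a patient with continuing long-term antibiotics is eligible. That choice is the sponsor's. If not, remove the exception and item 1 from 9.9. If so, print the exception against each criterion it overrides, including exclusion 17.
3. If they are eligible, flag these patients and repeat the primary microbiota comparison without them as a sensitivity analysis, named in section 12.3.

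The cost is protocol wording and one extra analysis on slightly fewer patients. No new data are needed: antibiotic use and dose are recorded at enrollment (section 11.1), and the Study Calendar collects concomitant medications at the follow-up calls, with the weekly samples and at one month.

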## 10. LABS

Tests will not be done in a CLIA-certified lab. Samples will be collected from the patient and brought to the lab while the subject is admitted. After discharge, the subject will mail the samples to the laboratory for processing. Samples will be labeled with only an ID number. We will not disclose any results to the patients. Data generated by the laboratory procedures will be used to determine the patient's colonization status with MDROs and *C. difficile* at baseline and to determine if colonization status changes during the course of the trial.

Laboratory procedures include:

- Bacterial DNA isolation from stool
- 16s rRNA sequencing of the v4 region
- Culture to identify MDROs, including but not limited to: MRSA, Vancomycin-resistant enterococcus (VRE), and *C. difficile*
- Polymerase Chain Reaction (PCR)

Data from laboratory procedures will also be used to determine if the FMT treatment has an impact on the patients gut microbiome. All stool remaining following the completion of laboratory procedures will be stored at -80°C and labeled with the sample ID and held for future analysis.

Up to one gram of stool will be sent to Finch therapeutics for additional 16s rRNA sequencing.

## 11. STUDY VISITS

### 11.1. Screening/Enrollment, and Baseline Visit

For some patients the screening, enrollment, and baseline visit should occur on the same day. However, the enrollment and baseline visit may be at a later time (though it must still be within the first 3 doses of the prescribed antibiotic window) if needed to meet the patient's needs.

#### *Screening: Will take place in a clinical setting*

Active screening. Any inpatient admitted to a non-ICU unit or outpatient presenting to any UWHC clinic (with a focus on patients presenting with CAP and UTI) meeting the enrollment criteria will be contacted about the study. Patients may also be identified through letters mailed to patients with a history of CDI in the last 90 days.

#### *Enrollment: Will take place in a clinical setting*

All patients with a history of CDI on antibiotics for any reason other than CDI meeting the eligibility criteria will be eligible for enrollment. Eligibility will be confirmed during the enrollment visit. Patients admitting with CAP and UTIs will be preferred. A detailed consent process will be administered by study staff who are trained in consenting procedures. Potential participants who fulfill the eligibility criteria will undergo a detailed clinical assessment by the research team which will include demographics, medical history, dietary

information and current medication. Data from this assessment may be from the participant/substitute decision maker, healthcare team and/or medical record.

- Data points at enrollment study visit:
  - General parameters:
    - Date of birth
    - Sex
    - Smoking status
    - Race
    - Ethnicity
    - Highest level of education
  - Past medical history and allergies
    - A focused collection of past medical history (including common infections)
  - Current medication list
    - Current antibiotic use, including dose
  - Dietary history
  - Social history
    - Alcohol, smoking history
  - Recent hospitalizations
  - Exposure to farm animals
  - Recent international travel history
  - Examination findings
    - Vital signs: temperature, height, weight, heart rate, blood pressure, O2 saturation if on chronic oxygen therapy. (Vital signs measurements at all time points may be abstracted from medical records if available.)
    - Relevant review of symptoms
  - Overall assessment of current health
  - Stool consistency (Bristol Stool Scale) and frequency
- Sample collection
  - Stool sample collected using a stool collection kit/hat and provided with patient diary
- Formal aspects
  - Informed consent procedure
  - Verification of inclusion and exclusion criteria including administering 'test' capsule and documenting:
    - Safe to receive intervention (yes/no)
    - Able to swallow test capsule (yes/no)

Immunocompromised patients at risk for CMV/EBV will have blood drawn for the EBV and CMV antibody test done by the UWHC lab. The blood draw will be done by a UWHC phlebotomist or their local lab if this is preferred by the patient. All costs will be covered by the study. Results will be released to the patient and included in their medical record.

*Baseline (Day 0): Will take place in a clinical setting*

After the baseline clinical assessment and stool sample have been collected, subjects in groups 1 and 3 (daily FMT and daily placebo) are eligible to undergo administration of the intervention (DE or placebo) in

accordance with the randomization schedule. The intervention will be administered by the blinded treatment staff and the participant observed for 30 minutes following administration. Post-ingestion observation of inpatients will only occur after the first dosing; subsequent inpatient dosing will be administered by a study physician/nurse but do not require 30 minutes of observation. Pre-intervention vital signs (as previously described) will be collected or abstracted from the medical record prior to first dose. Participants will be provided with information regarding monitoring for minor and severe adverse event related to the intervention administration. Participants will be encouraged to report any concerning symptoms to staff. Oral nutrition may commence 1 hour post-capsules administration. Study staff do not need to collect a blood sample to check for neutropenia prior to dosing.

For all patients, a baseline stool sample will be collected and all patients should begin to fill out their patient diary starting on Day 0. If a patient is unable to provide a stool sample, peri-rectal swabs may be collected.

## 11.2. Follow-up

Follow up will be different based on the group the patient is in.

### *Group 1 (daily FMT) and Group 3 (daily placebo): Will occur in a clinical setting for inpatients.*

Capsules will be delivered to the patients every day by a blinded member of the treatment team during the time they are admitted. If the patient is discharged or an outpatient, he/she will be provided with enough capsules to complete the study and will be asked to consume 5 capsules per day while on antibiotics as well as for 7 days post-antibiotic treatment completion. Outpatients and patients discharged during the follow-up period will be called or emailed (depending on patient preference) weekly to remind them to take their capsules as well as to send in their stool samples every three days (+/- 1 day). The researcher calling the subject will also ask the subject to count the number of pills he or she has remaining (recorded in the patient diary) and ask about any adverse events or changes to medications and diet. Study staff do not need to collect a blood sample to monitor for neutropenia. If the subject has any capsules remaining after completion of study intervention (e.g. missed doses, shortened antibiotic course after study intervention has been dispensed), the subject will be asked to return the remaining capsules to the Infectious Disease Research lab.

